### 7.4.5.1. Statistical Methodology Specification

Endpoint / Variables

 
Change from baseline in the respective iron parameter at each assessment visit
 

Model Specification

 
Analyses will be repeated for each iron parameter (ferritin/TSAT/hepcidin/serum iron/TIBC) using MMRM as follows:   <math display="block">\text{Iron}_{ik} = \beta_0 + \beta_{\text{baseline}} * \text{Baseline}_i + \beta_j + \beta_k + \beta_{jk} + \beta_{\text{baseline}^*j} * \text{Baseline}_i + \epsilon_{ik}</math> 
 <math>\text{Iron}_{i, \text{week}}</math>: each iron measurement for subject i at visit k  <math>\beta_0</math>: Intercept  <math>\beta_{\text{baseline}}</math>: baseline effect of each iron parameter  <math>\text{Baseline}_i</math>: the baseline value of each iron parameter for subject i  <math>\beta_j</math>: treatment effect (j= daprodustat, darbepoetin alfa)  <math>\beta_k</math>: visit effect (k = Week 4, Week 16, Week 28, Week 40, Week 52)  <math>\beta_{jk}</math>: treatment-by-visit interaction  <math>\beta_{\text{baseline}^*j}</math>: baseline-by-visit interaction  <math>\epsilon_{ik}</math>: random error for subject i at visit k  i: subject (i = 1, 2, ..., N)  N: number of subjects included in the analysis 
 
 
The model parameters will be estimated using Restricted Maximum Likelihood (method=REML) with the Newton-Raphson algorithm.
 
The Kenward-Roger method for calculating the denominator degrees of freedom will be used.
 
The variance-covariance structures for repeated measures within the individual subject will be unstructured (type=UN).
 
LS means for treatment j at visit k will be calculated as follows for each iron parameter as adjusted mean change from baseline.   <math display="block">\mu_{jk} = \beta_0 + \beta_{\text{baseline}} * \mu_{\text{baseline}} + \beta_j + \beta_k + \beta_{jk} + \beta_{\text{baseline}^*k} * \mu_{\text{baseline}}</math> 
 <math>\mu_{jk}</math>: LS mean for treatment j at visit k  <math>\mu_{\text{baseline}}</math>: mean for the baseline value of each iron parameter 
 
 
The treatment difference at visit k for model based mean change from baseline will be calculated as follows for each iron parameter as adjusted treatment difference   <math display="block">\mu_{\text{daprodustat}^*k} - \mu_{\text{darbepoetin alfa}^*k} = \beta_{\text{daprodustat}} - \beta_{\text{darbepoetin alfa}} + \beta_{\text{daprodustat}^*k} - \beta_{\text{darbepoetin alfa}^*k}</math> 
 
Note that log-transformed values will be used for TSAT and hepcidin in the MMRM analysis. The LS means for treatment j at visit k and the adjusted treatment difference at visit k will be exponentially back-transformed to the original scale and provided as follows:   Adjusted geometric mean percent change from baseline = <math>100 * (\exp(\mu_{jk}) - 1)</math>  Adjusted ratio for percent change from baseline = <math>\exp(\mu_{\text{daprodustat}^*k} - \mu_{\text{darbepoetin alfa}^*k})</math> 
 

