**Model Results Presentation**

- For ferritin, serum iron, and TIBC, the adjusted mean change from baseline will be presented with the associated 95% CIs by treatment at each assessment visit. The adjusted treatment difference (daprodustat – darbepoetin alfa) for change from baseline will also be presented with the associated 95% CI at each assessment visit.
- For TSAT and hepcidin, the adjusted geometric mean percent change from baseline will be presented with the associated 95% CIs by treatment at each assessment visit. The adjusted ratio (daprodustat / darbepoetin alfa) for percent change from baseline will also be presented with the associated 95% CI at each assessment visit.

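### SAP 7.4.5.1 names change from baseline as the iron endpoint but models the level and never subtracts baseline, so by-arm estimates read literally are levels labelled as changes

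*SAP*

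**What the plan says.** All of the following stand in the SAP 7.4.5.1 specification unless noted.

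- **Endpoint:** "Change from baseline in the respective iron parameter at each assessment visit".
- **Response:** "each iron measurement for subject i at visit k".
- **Scale:** "Note that log-transformed values will be used for TSAT and hepcidin in the MMRM analysis".
- **LS mean:** "LS means for treatment j at visit k will be calculated as follows for each iron parameter as adjusted mean change from baseline". In that formula baseline enters only through a covariate term evaluated at the "mean for the baseline value of each iron parameter".
- **By-arm back-transformation (TSAT, hepcidin):** "Adjusted geometric mean percent change from baseline", computed as `100*(exp(mu_jk) - 1)`.
- **Between-arm result (TSAT, hepcidin):** the exponentiated difference of LS means. The results paragraph of 7.4.5.1 describes it as follows: "The adjusted ratio (daprodustat / darbepoetin alfa) for percent change from baseline will also be presented".

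Three other places bear on this. SAP 5.2 defines percent change for TSAT, hepcidin and lipids from the within-subject difference of logs (post-dose minus baseline). SAP 7.4.2 commits to plotting the adjusted changes by arm over time. SAP 9.5.1 applies the 7.4.5.1 model, without logs, to the SF-36 scores, the EQ-5D-5L index and EQ-VAS, and also reports adjusted mean changes.

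**The concern.** The LS mean of a model for a measurement is a level. It becomes a change only if baseline has been subtracted, either from the response or from the LS mean. Section 7.4.5.1 does neither, yet it labels the LS mean a change and, for two parameters, applies a back-transformation that is valid only for a log ratio to baseline.

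The equation and the response wording follow the hemoglobin model in SAP 7.1.5.1. That model has the same form, but there the LS mean is correctly reported as a level.

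What is at stake is the by-arm output: the adjusted changes and their intervals at each visit, the plots over time, and the repeats by baseline iron use. These could disagree with descriptive tables of the same quantity built by the SAP 5.2 rule. For the quality-of-life scores, a level labelled as a change is less conspicuous than a TSAT change in the thousands of percent, so it is easier to miss.

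**Working it through.** The plan gives no figure to reproduce; the check is of the formulas.

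**Step 1: what the back-transformation returns.** Let GM_k be the adjusted geometric mean at visit k and GM_0 the geometric mean at baseline.

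- Response ln(value), as defined in 7.4.5.1: mu_jk = ln(GM_k), so `100*(exp(mu_jk) - 1)` = 100*(GM_k - 1). This depends on the unit of measurement.
- Response ln(value) - ln(baseline), as in SAP 5.2: mu_jk = ln(GM_k/GM_0), so the same expression is 100*(GM_k/GM_0 - 1), a true percent change.

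**Step 2: size.** The documents give no baseline geometric means, so these are assumed over a range. With a true change of 0%:

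| Parameter | Assumed geometric mean | Formula as written |
|---|---|---|
| TSAT | 15% | 100*(15 - 1) = +1400% |
| TSAT | 25% | 100*(25 - 1) = +2400% |
| TSAT | 40% | 100*(40 - 1) = +3900% |
| Hepcidin | 5 nmol/L | 100*(5 - 1) = +400% |
| Hepcidin | 40 nmol/L | 100*(40 - 1) = +3900% |

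A true fall of 20% from a TSAT of 25% gives 100*(20 - 1) = +1900%. For ferritin, serum iron and TIBC the by-arm value is too high by the mean baseline: an assumed ferritin mean of 150 at both times would be shown as +150 instead of 0. The quality-of-life scores would likewise be too high by their mean baseline score.

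**Step 3: the between-arm contrast.** Write B_i for the baseline on the response scale. The model contains B_i and its interaction with visit. Subtracting B_i from the response lowers the coefficient of B_i by 1 and changes nothing else: residuals, covariance estimates and treatment terms are the same. The by-arm LS means move by exactly the mean of B_i, and the contrasts and their standard errors do not move.

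**Step 4: numerical check.** I simulated TSAT on assumed values: 270 subjects randomized 1:1, five visits, log baseline centred on ln 25 with SD 0.35, residual variance 0.09 with correlation 0.5, monotone dropout with an expected 75% completing. The 7.4.5.1 mean model with a logged baseline covariate and an unstructured covariance was fitted by maximum likelihood to each response.

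| Week 52 result | Response ln(value) | Response ln(value) - ln(baseline) |
|---|---|---|
| Daprodustat LS mean | 3.13047 | -0.06221 |
| Back-transformed | +2188.5% | -6.0% |
| Ratio between arms | 0.9395 | 0.9395 |

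The LS means differ at every visit by 3.1927, the mean ln(baseline). Treatment differences and standard errors agree to 3e-14.

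**Step 5: the condition in Step 3.** It requires the covariate to be on the response scale. For TSAT and hepcidin, 7.4.5.1 says logged values are used in the model but describes the covariate only as the baseline value. If baseline were left unlogged, ln(baseline) would not be a linear function of the covariate, and the log-level and log-change models need not give the same contrast.

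**The case against.** The strongest reply is that the intended response can be recovered from the SAP. The endpoint row, the strategy in 7.4.4, the results paragraph and the revision history all name change from baseline. SAP 7.4.2 sends TSAT and hepcidin to SAP 5.2, which gives the log-difference recipe. With that response, the label and the back-transformation are both correct. Descriptive change tables are also planned, and a TSAT error of this size would stand out beside them. The statement that log-transformed values are used may reasonably be read to cover the baseline covariate too.

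Most of this stands. It shows that change was intended, so a reader might infer that the delivered tables will be wrong; the documents do not support that. A programmer who follows the endpoint row would get it right, and the mock shells are in separate documents not available here. What remains is that the response definition, the one line that says what to model, says something else, and correct output depends on departing from it.

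Three other stronger readings also fail. One is that the comparison of arms is biased: Steps 3 and 4 show it is unchanged under the stated condition. Another is that this is the trial's key biomarker comparison: the documents class iron metabolism as exploratory and place it outside the testing sequence. The third is that the between-arm ratio is miscalculated. With assumed falls of 30% and 10%, the SAP formula gives 0.70/0.90 = 0.78, a valid ratio of geometric mean ratios to baseline. A reader of the label might expect (-30%)/(-10%) = 3.0, but no SAP formula computes that, so only the label needs changing.

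**Conclusion.** The point holds as an internal contradiction in the specification. Read literally, 7.4.5.1 yields by-arm levels presented as changes for all five iron parameters and, through 9.5.1, for the quality-of-life scores. For TSAT and hepcidin with no true change, the reported percent change would be between +400% and +3900% over the assumed baselines; for the other parameters the excess equals the mean baseline. The percentages rest on assumed baselines and on the literal reading. The constant shift in the LS means does not depend on the assumed baseline values, given a covariate on the response scale.

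The consequence is limited to by-arm estimates, intervals and plots of exploratory and patient-reported endpoints. Between-arm contrasts are unaffected provided the covariate is on the response scale, and the primary and principal secondary conclusions do not change.

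**What to change.** In SAP 7.4.5.1:

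- For ferritin, serum iron and TIBC, define the response as `Iron_ik - Baseline_i`.
- For TSAT and hepcidin, define the response as `ln(Iron_ik) - ln(Baseline_i)`, with `ln(Baseline_i)` as the covariate.
- State in 9.5.1 that the response for each quality-of-life parameter is the change from baseline.

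Two editorial corrections belong with these. Index the baseline interaction in the model line by visit k, as the LS-mean formula and the term's own description already do. Label the exponentiated between-arm difference as the ratio of geometric mean ratios to baseline.

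The cost is a few lines of SAP text and a check of the response and covariate in the iron and quality-of-life programs. It needs no new data, and the between-arm estimates stay the same where the covariate is already on the response scale.

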
**Model Checking & Diagnostics**

- In case there is a problem with convergence of the unstructured (type=UN) variance-covariance, the following strategy will be examined.
  1. Use Fisher's scoring algorithm for the estimation method.
  2. Set Heterogeneous Toeplitz (type=TOEPH) structure for variance-covariance structure.
  3. In the event of that this model still fails to converge, alternative correlation structures may be considered such as type=CSH or CS.

**Model Results Presentation**

- For ferritin, serum iron, and TIBC, the adjusted mean change from baseline will be presented with the associated 95% CIs by treatment at each assessment visit. The adjusted treatment difference (daprodustat – darbepoetin alfa) for change from baseline will also be presented with the associated 95% CI at each assessment visit.
- For TSAT and hepcidin, the adjusted geometric mean percent change from baseline will be presented with the associated 95% CIs by treatment at each assessment visit. The adjusted ratio (daprodustat / darbepoetin alfa) for percent change from baseline will also be presented with the associated 95% CI at each assessment visit.

**Subgroup Analyses**

- For all of the respective iron parameter, the above analysis will be repeated by baseline iron use subgroup (See Section [5.4.2](#)) in the same manner.
- The subgroup analyses will be based on the ITT population.
- If there is a problem with convergence for a subgroup, the result of the subgroup will not be displayed.

## 8. SAFETY ANALYSES

The safety analyses will be based on the Safety population, unless otherwise specified.

### 8.1. Adverse Events Analyses

Adverse events analyses including the analysis of adverse events (AEs), serious adverse events (SAEs), and other significant AEs will be based on GSK Core Data Standards. The details of the planned displays are provided in [Appendix 10: List of Data Displays](#).

Medical device incidents fulfilling the definition of an AE/SAE will follow the same processes for collecting AE and SAE information and will not be summarized particularly.

Endpoint / Parameter/ Display Type	Absolute		
	Summary		Individual
	T	F	L
Adverse Events (AEs)			
On-Therapy AEs by SOC and PT	Y		Y
On-Therapy AEs by SOC and PT and Maximum Intensity	Y		
On-Therapy AEs by SOC and PT by onset	Y		
On-Therapy AEs up to Week 4 by SOC and PT	Y		
On-Therapy AEs up to Week 4 by SOC and PT and Maximum Intensity	Y		
Post-Therapy AEs by SOC and PT	Y		Y
Post-Therapy AEs by SOC and PT and Maximum Intensity	Y		
On-Therapy Drug-Related AEs by SOC and PT	Y		
On-Therapy Drug-Related AEs by SOC and PT and Maximum Intensity	Y		
On-Therapy Drug-Related AEs up to Week 4 by SOC and PT	Y		
On-Therapy Drug-Related AEs up to Week 4 by SOC and PT and Maximum Intensity	Y		
Post-Therapy Drug-Related AEs by SOC and PT	Y		
Post-Therapy Drug-Related AEs by SOC and PT and Maximum Intensity	Y		
On-Therapy Common (>= 2 %) AEs by Overall Frequency	Y	Y 	
On-Therapy Common (>= 5 %) Non-Serious AEs by SOC and PT (Subjects & No. of Occurrences)	Y		
On-Therapy Non-Serious Drug-Related AEs	Y		
Subject Numbers for Individual AEs			Y
Relationship Between AE SOC, PT & Verbatim Text			Y
Serious and Other Significant AEs			
Fatal Serious AEs			Y
Non-Fatal Serious AEs			Y
On-Therapy Serious AEs	Y		
Post-Therapy Serious AEs	Y		
On-Therapy Serious Drug-Related AEs	Y		
Serious AEs in Screening Period 			Y
Reasons for Considering as a Serious AE			Y
On-Therapy Serious AEs by SOC and PT (Subjects & No. of Occurrences)	Y		
AEs Leading to Withdrawal from Study / Permanent Discontinuation of Study	Y		Y

Endpoint / Parameter/ Display Type	Absolute		
	Summary		Individual
	T	F	L
Treatment by SOC and PT			
CV Events			Y

**NOTES:**

- T = Table, F = Figures, L = Listings, Y = Yes display generated, SOC = System Organ Class, PT = Preferred Term.
- Summary = Represents TF related to any summaries (i.e. descriptive statistics) of the observed raw data.
- Individual = Represents FL related to any displays of individual subject observed raw data.

[1] Plot of common AEs and relative risk will be generated by treatment.

[2] Listing will be based on All Screening Population.

### 8.1.1. Planned Adverse Events Analyses Displays

- **Adverse Events**

#### AEs by SOC and PT

The number and percentage of subjects reporting at least one AE will be provided by treatment group. These events will be summarized by primary system organ class and preferred term. On-therapy AEs, on-therapy AEs up to Week 4, and post-therapy AEs will be summarized separately.

On-therapy AEs by onset ( $\leq$ Week 4,  $>$ Week 4 to  $\leq$ Week 16,  $>$ Week 16 to  $\leq$ Week 28,  $>$ Week 28 to  $\leq$ Week 40,  $>$ Week 40) will also be summarized separately. The number of subjects reporting the first occurrence of each AE will be provided by onset time by primary system organ class and preferred term.

#### AEs by SOC and PT and Maximum Intensity

AEs will be summarized by treatment group; by maximum intensity (not applicable, mild, moderate, severe) by primary system organ class and preferred term. Subjects who experience the same event several times with different intensities will only be counted with the maximum intensity in the order of (not applicable  $<$  mild  $<$  moderate  $<$  severe). On-therapy AEs, on-therapy AEs up to Week 4, and post-therapy AEs will be summarized separately.

#### Drug-Related AEs by SOC and PT

The number and percentage of subjects reporting at least one drug-related AE will be provided by treatment group. These events will be summarized by primary system organ class and preferred term. On-therapy AEs, on-therapy AEs up to Week 4, and post-therapy AEs will be summarized separately.

#### Drug-Related AEs by SOC and PT and Maximum Intensity

Drug-related AEs will be summarized by treatment group; by maximum intensity (not applicable, mild, moderate, severe) by primary system organ class and preferred term.

Subjects who experience the same event several times with different intensities will only be counted with the maximum intensity in the order of (not applicable < mild < moderate < severe). On-therapy, up to Week 4, and post-therapy AEs will be summarized separately.

On-Therapy Common ( $\geq 2\%$ ) AEs by Overall Frequency

The number and percentage of subjects with on-therapy common ( $\geq 2\%$  in any treatment group) adverse events by overall frequency will be provided by treatment group. These events will be summarized by preferred term.

A graph will be produced which displays both AE incidence rates and relative risks.

On-Therapy Common ( $\geq 5\%$ ) Non-Serious AEs by SOC and PT (Subjects & No. of Occurrences)

The number and percentage of subjects reporting at least one on-therapy common ( $\geq 5\%$  in any treatment group) non-serious AE will be provided by treatment group. The number of on-therapy non-serious AE occurrences will also be provided. These events will be summarized by primary system organ class and preferred term.

On-Therapy Non-Serious Drug-Related AEs

The number and percentage of subjects with on-therapy non-serious drug-related AEs will be summarized by preferred term.

- **Serious and Other Significant AEs**

Serious AEs

The number and percentage of subjects reporting at least one Serious AE will be provided by treatment group. These events will be summarized by primary system organ class and preferred term. On- and post-therapy serious AEs will be summarized separately.

On-Therapy Serious Drug-Related AEs

The number and percentage of subjects with on-therapy serious drug-related AEs will be summarized by preferred term.

On-Therapy Serious AEs by SOC and PT (Subjects & No. of Occurrences)

The number and percentage of subjects reporting at least one on-therapy serious AE will be provided by treatment group. The number of on-therapy serious AE occurrences will also be provided. These events will be summarized by primary system organ class and preferred term.

*AEs Leading to Withdrawal from Study / Permanent Discontinuation of Study Treatment by SOC and PT*

The number and percentage of subjects reporting an on-therapy AE leading to discontinuation of study treatment will be summarized by treatment group. These events will be summarized by primary system organ class and preferred term.

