4.2. Treatment Groups and Study Periods

Details for each study period and treatments are described below. In this study, a point-of-care Hgb analyzer (HemoCue®) will consistently be utilized for confirmation of subjects' eligibility, withdrawal criteria and dose adjustments of study medication.

Screening phase

Subjects who have provided informed consent and meet all of the eligibility criteria at screening (Week -4~-2) (Sections 5.1 and 5.2) will be provisionally enrolled in the study. Subjects who have used oral iron since before the start of the study must remain on the same regimen throughout the screening phase (intravenous iron will not be allowed). Subjects will also continue to use ESA throughout the screening phase. The regimen of ESA therapy should remain unchanged throughout the screening phase.

Treatment phase

Subjects who meet all of the eligibility criteria at the start of the treatment phase (Day 1) will be randomized in a 1:1 ratio to receive daprodustat or darbepoetin alfa and enrolled in the study. Subjects will be ESA users and will switch their ESA therapy to darprodustat at Day 1 so that the randomization date (Day 1) should coincide, as closely as possible, with the date of next scheduled ESA administration. In accordance with the randomization instructions, subjects randomized to the daprodustat group will receive daprodustat and darbepoetin alfa matching placebo for 52 weeks. Subjects randomized to the darbepoetin alfa group will receive daprodustat matching placebo and darbepoetin alfa for 52 weeks. Daprodustat will be orally administered once daily, and darbepoetin alfa will be intravenously administered once weekly. In both groups, dose adjustments for study medication during the treatment phase will be made according to the administration schedule specified in Section 6.4 to achieve and/or maintain Hgb within the target range (10.0-12.0 g/dL). In addition, supplemental iron therapy will be administered according to the standard initiation criteria as described in Section 6.12. It should be noted that intravenous iron or dose change for oral iron will not be allowed from Day 1 to Week 4.

Follow-up phase

Subjects will visit the site for follow-up assessments and observations 2 weeks after the completion/discontinuation of study treatment. During the follow-up phase, treatment of renal anemia will be allowed as necessary at the discretion of the investigator (or subinvestigator).

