4.3. Study Subjects and Number of Subjects

A total of 270 subjects will be randomized (daprodustat group: 135 subjects, darbepoetin alfa group: 135 subjects). Assuming a dropout rate of 30% during the screening phase, approximately 386 subjects need to be screened. Assuming a dropout rate of 25% after the start of study treatment, a total of 202 subjects are expected to complete the 52-week treatment.

Table 1 Target Number of Subjects

Screened	386
Randomized/enrolled	270
Completed 52-week treatment	202

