5.4. Permanent discontinuation of study treatment and study withdrawal

If subjects meet one of the following criteria, study treatment should be permanently discontinued and subjects will be withdrawn from the study. The withdrawal reason should be recorded.

- Hgb < 7.5 g/dL
 - Note: HemoCue Hgb values will be employed. If an initial Hgb value meets the Hgb stopping criteria, measurement will be repeated at the same study visit (using the same sample) to calculate the average. If the average meets the Hgb stopping criteria, study treatment will be discontinued.
- Kidney transplant
- Subject becomes pregnant or intends to become pregnant during the study.
- Diagnosis of new or recurrent cancer
- Liver chemistry abnormalities exceeding the threshold criteria (see Section 5.4.1.)
- Need for chronic (more than 14 days) use of prohibited medication (strong inhibitors/ inducers of CYP2C8 meet this criteria)
- When the investigator (or subinvestigator) considers necessary to withdraw the subject from the study for other reasons

Subjects who meet any of the withdrawal criteria or are withdrawn for other reasons during the treatment phase should be assessed at withdrawal visit after study treatment is discontinued, and will then enter the follow-up phase.

Should a subject fail to attend a required study visit, the investigator (or subinvestigator) should take the following measures:

- The investigator (or subinvestigator) or designee should attempt to contact the subject and reschedule the missed visit as soon as possible.
- The investigator (or subinvestigator) should counsel the subject on the importance of maintaining the assigned visit schedule and determine whether the subject is willing to continue his/her participation in the study and/or whether the subject should remain in the study.
- The investigator (or subinvestigator) or designee should make every effort to regain contact with a subject who is deemed "Lost to Follow-up". All efforts to contact the subject should be documented in the subject's clinical charts.
- Should the subject continue to be unreachable, then and only then will he/she be considered "Lost to Follow-up."

[figure not shown]
A subject may withdraw from the study at any time at his/her own request. The investigator (or subinvestigator) may withdraw a subject from the study at any time for safety or compliance reasons or study conduct considerations. If a subject withdraws from the study, he/she may request destruction

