7.4.1.1. Time period and Frequency for collecting AE and SAE information

• AEs and SAEs will be collected from the start of Study Treatment until the follow-up contact (see Section 7.4.1.3.), at the timepoints specified in the Time and Events Table (Table 10).

- Medical occurrences that begin prior to the start of study treatment but after obtaining informed consent may be recorded on the Medical History/Current Medical Conditions section of the CRF.
- Any SAEs assessed as related to study participation (e.g., protocol-mandated procedures, invasive tests, or change in existing therapy) or related to a GSK product will be recorded from the time a subject consents to participate in the study up to and including any follow-up contact.
- All SAEs will be recorded and reported to GSK within 24 hours, as indicated in Section 12.6.

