#### 15.4.1.2. Study Phases for AE Data

On-therapy AEs will be treated as treatment emergent AEs, therefore, treatment emergent flag for AEs will be derived from on-therapy treatment state.

Treatment State	Definition
Pre-therapy	AE Start Date < Randomization Date
On-therapy	Randomization Date ≤ AE Start Date ≤ Treatment Stop Date + 1 day
Post-therapy	AE Start Date > Treatment Stop Date + 1 day
Duration (Days)	AE Resolution Date – AE Onset Date + 1 day
Drug-related	If relationship is marked 'YES' on eCRF or value is missing.

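### On-therapy AE comparisons use crude percentages and relative risks with no person-time rate beside them, so they would favour the arm with less exposure if withdrawals differ between arms

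*SAP*

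**What the plan says.** - **Stopping and leaving.** Under Protocol 5.4, when a listed criterion is met, "study treatment should be permanently discontinued and subjects will be withdrawn from the study". Protocol 4.2 gives one further contact: "Subjects will visit the site for follow-up assessments and observations 2 weeks after the completion/discontinuation of study treatment". AE collection ends there (Protocol 7.4.1.1).
- **On-therapy window.** SAP 15.4.1.2 defines an on-therapy AE by "Randomization Date ≤ AE Start Date ≤ Treatment Stop Date + 1 day". Post-therapy AEs are summarized separately.
- **Expected attrition.** Protocol 4.3: "Assuming a dropout rate of 25% after the start of study treatment", 202 of 270 subjects are expected to complete. No figure is given by arm.
- **Summary measure.** SAP 8.1.1: "The number and percentage of subjects reporting at least one AE will be provided by treatment group". SAEs (8.1.1) and AESIs (8.2.1) are summarized in the same way.
- **Between-arm measure.** For common on-therapy AEs, SAP 8.1.1 states that "A graph will be produced which displays both AE incidence rates and relative risks". In SAP 15.10.4.5 this is Figure 3.1, sorted by relative risk. The SAP does not define its incidence rates as being per unit of time.
- **Onset table.** SAP 8.1.1: "The number of subjects reporting the first occurrence of each AE will be provided by onset time by primary system organ class and preferred term". The intervals are up to Week 4, three 12-week intervals to Week 40, and after Week 40. No number at risk is mentioned.
- **Exposure.** Time on study treatment is derived in SAP 15.6.2 and tabulated under SAP 6.2. It is not linked to the AE counts.

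**The concern.** Each subject's on-therapy window is as long as their time on treatment. A crude percentage treats a subject observed for 8 weeks like one observed for 52. A relative risk of two such percentages therefore mixes the event rate with the length of observation. If one arm loses more subjects, or loses them earlier, it accumulates fewer events for that reason alone. In the onset table, later intervals can look quieter simply because fewer subjects remain on treatment.

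Safety against darbepoetin alfa is a stated objective of a pivotal study (Protocol 2.1 and 3). Earlier daprodustat studies ran for up to 24 weeks (Protocol 4.6.3), so the later months are where this trial adds most and where the group at risk is smallest. The SAP sets strategies for study withdrawal in the efficacy analyses (7.1.4, 7.2.4) and divides IV iron dose by time on treatment (15.6.6). Section 8 has no equivalent for AEs.

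**Working it through.** **The plan's own figure.** 270 × (1 − 0.25) = 202.5, against 202 stated in Protocol 4.3. It reproduces.

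**Inputs.** From the documents: 25% dropout overall, 1:1 allocation, 52 weeks, and a window that closes at treatment stop + 1 day. Assumed here: the split between arms, the timing of dropout, and a constant event rate L that is equal in both arms (true ratio 1.0).

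**Formulas, per subject and with time in years.** Let p be the dropout proportion. Dropout times are uniform on (0, a), with a = 1 if spread over 52 weeks and a = 16/52 if confined to the first 16 weeks. The extra day is ignored here.
- Person-time on treatment = (1 − p) + p × a/2
- Crude proportion with an event = (1 − p)(1 − e^(−L)) + p × [1 − (1 − e^(−La))/(La)]

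**Dropout spread over 52 weeks, 20%/30%.**
- Person-time: 0.80 + 0.20 × 0.5 = 0.90 against 0.70 + 0.30 × 0.5 = 0.85. The ratio is 0.944, or 5.6% less.
- With L = 0.3: 1 − e^(−0.3) = 0.2592, and the mean for dropouts is 0.1361. Crude proportions are 0.80 × 0.2592 + 0.20 × 0.1361 = 23.46% and 0.70 × 0.2592 + 0.30 × 0.1361 = 22.22%. The crude relative risk is 0.947.
- For L from 0.1 to 1.0 it runs from 0.945 to 0.954.

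**Dropout in the first 16 weeks, 20%/30%.**
- Mean stopping time is 8/52 = 0.154. Person-time is 0.831 against 0.746, a ratio of 0.898, or 10.2% less.
- With L = 0.3: crude proportions are 21.63% and 19.49%, relative risk 0.901. The range for L from 0.1 to 1.0 is 0.899 to 0.908.

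**Other cases.**
- 25%/25% with the same timing: 1.00 for every L.
- 15%/35%: 0.89–0.91 if spread over 52 weeks, 0.81–0.82 if early.
- Timing alone (25% in both arms, all at Week 12 in one and all at Week 40 in the other, 10% 52-week AE risk): 0.86.

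**Check with another dropout model.** Exponential withdrawal, with the window at treatment stop + 1 day and a 10% 52-week AE risk, gives 0.94 at 20%/30% and 0.88 at 15%/35%. Extending the window to 14 days after stop gives 0.94 and 0.89, so the tail hardly matters. In this model a true hazard ratio of 1.50 in the arm with more dropout appears as a crude relative risk of 1.46 at 25%/25%, and as 1.29 when that arm loses 35% and the other 15%.

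**With the fix.** Under a constant rate, expected person-time to first event equals the crude proportion divided by L. For the first case with L = 0.3 this is 0.2346/0.3 = 0.782 and 0.2222/0.3 = 0.741 years per subject. The rates are 0.2346/0.782 = 0.30 and 0.2222/0.741 = 0.30 per year, a ratio of 1.00.

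**The case against.** **The bias is conditional.** This stands. Treatment is randomized, double-blind and double-dummy, with the same withdrawal criteria in both arms, and the 25% is not split. The 20%/30% and 15%/35% splits are assumptions; the second is a 20-point gap.

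**Unequal early stopping is not shown.** A reader might infer it from the difference in starting regimens: one fixed daprodustat dose held to Week 4, against a converted darbepoetin dose adjustable from Week 2. The documents do not support that as an expectation. Protocol 4.5 reports simulations and clinical data suggesting that Hgb is maintained for 4 weeks after the switch. Entry requires Hgb of at least 9.5 g/dL, and the only Hgb criterion listed for withdrawal is below 7.5 g/dL. High Hgb leads to interruption, not withdrawal. The 16-week scenario is an illustration only.

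**The relative risk does not cover AESIs as a category.** Figure 3.1 is for common AEs. AESIs are selected at patient level and reported as number and percentage (SAP 8.2, 8.2.1). It would be wrong to say that the plan forms relative risks for them; only their crude percentages are affected.

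**Imbalance would be visible.** Exposure, disposition by reason, AEs leading to discontinuation, AEs to Week 4 and AEs by onset are all tabulated. That is true, but none of these corrects the percentages or relative risks. An AE that itself causes withdrawal is still counted, so only later events are missed.

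**Sampling error is larger.** At 135 per arm and 10% incidence, SE(log RR) = √[2 × (1/13.5 − 1/135)] = 0.365, giving a 95% CI around 1.0 of about 0.49 to 2.05. Safety is also descriptive, with no test. Both points limit the weight of the concern but do not justify omitting the rates.

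**The mock shells are separate documents.** Figure 3.1 and Table 3.5 may show more than the SAP text says. The point is that the SAP states no person-time denominator and no number at risk.

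**Conclusion.** The point holds in a conditional form. The plan has no person-time rate for AEs, its on-therapy window closes one day after treatment stop, and a quarter of subjects are expected to stop early. If withdrawals differ by arm in number or timing, the crude comparisons favour the arm with less exposure: a relative risk of about 0.95 for an assumed 20%/30% split spread over the year, about 0.90 if dropout is early, and 1.00 if both arms lose subjects alike. These figures rest on a constant, equal event rate and on assumed splits and timing.

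Two stronger readings should be avoided. One is that the planned comparison is already biased, or biased towards daprodustat: nothing in the documents says which arm will lose more subjects. The other is that the two-week follow-up limit drives Figure 3.1: post-therapy AEs are outside that figure. This is an inexpensive improvement to the SAP, not a defect that invalidates the safety analysis.

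**What to change.** In SAP 8.1.1 and 8.2.1, keep the crude n (%) and relative risks, and make these additions before unblinding:

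1. **Tables 3.1, 3.15, 3.17 and 3.22:** the number of subjects with an event per 100 person-years. Person-time runs from randomization to first event or, if there is none, to the end of the existing on-therapy window in SAP 15.4.1.2, so that numerator and denominator match.
2. **Figure 3.1:** the rate ratio with its 95% CI alongside the relative risk.
3. **Table 3.5:** the number of subjects still on treatment at the start of each onset interval.
4. **Footnotes:** for withdrawals on darbepoetin alfa the stop date is not captured in the eCRF and is derived as last injection + 6 days (SAP 15.6.1). Their on-therapy window therefore runs to 7 days after the last injection, whereas the daprodustat window runs to 1 day after the recorded stop date. State also that the rates assume a roughly constant hazard and do not correct for informative withdrawal.

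The cost is extra columns in four tables, additions to one figure and one further table, and modest programming from dates already recorded or derived. Trial conduct does not change.
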